Title of Study Protocol: **Fish oils and Adipose Inflammation Reduction (FAIR Study)**

Principal Investigator: **[name], MsTR**

Sponsors of Protocol: **National Institutes of Health**

Grants: **1K23DK095913-01A1 (NIDDK): Omega-3 PUFA suppress adipochemokines (PI:[name])**

IRB Protocol Number: **818359**

Date of Document: **November 4, 2014**

Synopsis

Title	Fish oils and Adipose Inflammation Reduction (FAIR Study)
Short Title	FAIR Study
Protocol Number	818359
Study Design	Parallel arm, double blind, placebo-controlled trial
Study Center(s)	University of Pennsylvania Medical Center Philadelphia, PA USA
Objective	To examine the effect of omega-3 fish oil supplementation
Study Population, Diagnosis And Main Inclusion Criteria	Obese (BMI>30), non-diabetic men and non-pregnant/non-lactating women aged 18-50 not currently consuming significant amounts of omega 3 fatty acids.
Study Product, Dose, Route, Regimen, Duration of administration	Participants will be randomized to placebo of Lovaza 4 grams/day orally. Subjects will be treated for 8 weeks.
Reference therapy	Placebo
Pharmacodynamic Evaluations	Inflammatory markers (cytokines, chemokines, acute phase proteins), metabolic markers, oral microbiome composition, monocyte function and lipoproteins
Safety Evaluations	Clinical and laboratory measurements will be taken at screening and upon completion of the study.
Statistical Methodology	Analysis will compare within group and between group differences to determine effect of omega 3 fatty acids vs placebo on all measures indicated

1.0 ETHICAL CONSIDERATIONS

The study will be conducted in accordance with the University of Pennsylvania's clinical research standards that meet regulations relating to Good Clinical Practice (GCP).

These standards adhere to the following guidelines:

- Good Clinical Practice: ICH Consolidated Guideline (International Conference on Harmonization of Technical Requirements for the Registration of Pharmaceuticals for Human Use, May 1996).
- United States (US) Code of Federal Regulations (21 CFR) dealing with human subject protection and conduct of investigational clinical studies (21 CFR parts 50, 54, 56, 312, and 314).
- Declaration of Helsinki, concerning medical research in humans ("Recommendations Guiding Physicians in Biomedical Research Involving Human Subjects," Helsinki 1964, amend Tokyo 1975, Venice 1983, Hong Kong 1989, revised version of Somerset West, Republic of South Africa, October, 1996 and Scotland, 2000).

This protocol and any amendments will be submitted to University of Pennsylvania institutional Review Board (IRB), in agreement with local legal prescriptions, for formal approval of the study conduct. The decision of the IRB concerning the conduct of the study will be made in writing to the investigator before commencement of this study.

All subjects for this study will be provided a consent form describing this study and providing sufficient information for subjects to make an informed decision about their participation in this study. The consent form will be submitted with the protocol for review and approval by the IRB for the study. The formal consent of a subject, using the IRB-approved consent form, must be obtained before that subject is submitted to any study procedure. This consent form must be signed by the subject or legally acceptable surrogate, and the investigator-designated research professional obtaining the consent.

2.0 INTRODUCTION AND BACKGROUND

Adipose inflammation, induced by inflammatory leukocyte infiltration, is a crucial link between obesity and its metabolic complications^{1-3 2-8 9-12}, including insulin resistance, type 2 diabetes, and metabolic syndrome. Chemokine pathways including monocyte chemoattractant protein (CCL2) and fractalkine (CX3CL1) and their receptors CCR2 and CX3CR1 may modulate insulin resistance by regulating adipose macrophage recruitment and activation^{4,13-15}. Variable expression of CCR2 and CX3CR1 is a critical determinant of monocyte survival and inflammatory state and delineates two populations: pro-inflammatory CX3CR1^{lo}CCR2⁺ monocytes associated with classically-activated, inflammatory (M1) adipose macrophages vs. less inflammatory CX3CR1^{hi}CCR2⁻ thought to give rise to alternatively-activated (M2) adipose macrophages¹⁻³. Metabolic and inflammatory stimuli associated with obesity induce release of chemokines that promote disproportionate migration and adhesion of pro-inflammatory CX3CR1^{lo}CCR2⁺ monocytes and/or shift of M2 to M1 macrophages¹⁶.

Omega-3 polyunsaturated fatty acids: Murine LC n-3 PUFA, from fish and fish oil supplements, include eicosapentaenoic acid (EPA) and docosahexaenoic acid (DHA), and are used clinically to treat dyslipidemia. Decreased triglycerides with increased HDL is seen and adiponectin levels are increased in mice and humans on LC n-3 PUFA^{17,18}. Data assessing beneficial effect of LC n-3 PUFA on incidence of cardiovascular disease is conflicting^{19,20}. Several large scale studies have reported benefits of LC n-3 PUFA in primary^{21, 22, 23} and secondary^{24, 25} prevention of adverse cardiovascular outcomes; however, the recently completed ORIGIN trial showed no reduction in cardiovascular death in a large cohort of dysglycemic subjects receiving 1 gram LC n-3 PUFA vs. placebo²⁶. Dose, treatment duration, and underlying disease burden may underlie this discrepancy²⁷.

LC n-3 PUFA reduce obesity-related inflammation: LC n-3 PUFA themselves or anti-inflammatory metabolites they produce exert pleiotropic anti-inflammatory effects in human and animal models²⁸. In patients with chronic inflammatory diseases, LC n-3 PUFA reduce systemic inflammation²⁹⁻³²; remarkably, decreases in inflammatory markers are also suggested with LC n-3 PUFA in the low-grade inflammatory condition of obesity³³. In a trial of 25 adolescents with metabolic syndrome, 3 weeks of LC n-3 PUFA supplementation decreased circulating lymphocytes and monocytes as well as levels of cytokines TNF α , IL-1 β , and IL6 despite no improvement in weight or insulin sensitivity³⁴.

LC n-3 PUFA reduce monocyte inflammatory state and ATM infiltration: Dietary studies in humans suggest that LC n-3 PUFA reduce monocyte inflammatory mediators^{35,36}, monocyte migration and adhesion, and receptor expression (CD44 variants)^{37,38}. Human THP-1 macrophages treated with LC n-3 PUFA *in vitro* had decreased LPS-stimulated cytokine expression (TNF α , IL-1 β , IL6) and inflammatory transcription factor nuclear factor kappa beta (NF κ B) activity³⁹. In mice, adding LC n-3 PUFA to diet reduced circulating Ly6C^{hi} inflammatory monocytes⁴⁰. In rodents fed a high fat diet (HFD), addition of LC n-3 PUFA prevents inflammatory ATM infiltration, adiponectin decrease, and inflammatory gene expression (including chemokines CCL2 and CCL5)^{41, 42 43,44 45}.

LC n-3 PUFA may attenuate NF κ B signaling: Though multiple mechanistic models are proposed, the NF κ B pathway is consistently implicated in reduced inflammation by LC n-3 PUFA²⁸. NF κ B signaling is downstream of TLR4 and cytokine receptor activation⁴⁶. *In vitro* LC n-3 PUFA is shown to inhibit LPS-induced activation of NF κ B and I κ B phosphorylation in macrophages, with associated reduction in inflammatory cytokines⁴⁷ and increased production of anti-inflammatory marker IL10⁴⁸.

GPR120 is a LC n-3 PUFA receptor and may inhibit NFκB signaling: Recent work suggests the effects of LC n-3 PUFA on obesity-related inflammation are mediated via interactions GPR120, a G-protein-coupled receptor (GPR), which is highly expressed on adipocytes and macrophages⁴⁹. GPR120 is part of the G α q-linked GPR family and stimulation results in increased intracellular Ca⁺⁺ and ERK activation⁵⁰. Compared to wild-type mice GPR120 deficient mice fed a HFD have increased weight, insulin resistance, circulating and adipose inflammatory markers—including the chemokine CCL2, and ATMs⁵¹. Remarkably, humans with a dominant-negative loss-of-function variant in *GPR120* (R270H) have increased incidence of obesity⁵¹. In 3T3-L1 adipocytes, siRNA knockdown of GPR120 reduced expression of insulin signaling genes⁵². Highlighting its role as an LC n-3 PUFA receptor, GPR120 deficiency blocks the benefits of LC n-3 PUFA supplementation to HFD in mice, agonists to GPR120 mimic effects of DHA to block LPS-induced NFκB activation in macrophages, and knockdown of GPR120 abolishes DHA effects⁴⁹. Whether GPR120 deficiency modulates EPA effects is not reported, notably anti-inflammatory effects of EPA occur via distinct changes in plasma cell membranes in immune cells⁵³.

LC n-3 PUFA may affect the oral microbiome

Periodontal disease has been associated with increased risk of cardiometabolic diseases^{54,55}. There is data that suggests that dietary fat intake, including omega-3 fatty acids affect the composition of the intestinal and oral microbiome^{56,57}. The direct effect of LC n-3 PUFA supplementation on oral microbiome composition and the relationship between inflammatory chemokine pathways and the microbiome have not previously been evaluated.

Overall LC n-3 PUFA modulate chemokine signaling including adipocyte and macrophage inflammation, ATM infiltration, and monocyte activation; these actions may be mediated, at least partially, via GPR120 and NFκB. However, no human studies examining the effect of LC n-3 PUFA on the CCL2 and CX3CL1 adipochemokine pathways have been reported and the role of GPR120 and NFκB on these pathways has not been explored. Insight into LC n-3 PUFA action on these functional pathways may clarify mechanisms and guide therapeutic developments in human.

We propose a clinical trial to assess the validity of LC n-3 PUFA as an adjuvant treatment in prevention of obesity-related adipose inflammation and metabolic disturbance. While clinical studies of LC n-3 PUFA show decreased systemic inflammation, and animal models demonstrate decreased adipose inflammation, the effect of LC n-3 PUFA on *human* adipose inflammation chemokine signaling and GPR120/NFκB activity in obesity have not been explored. We will utilize a double-blind placebo-controlled trial of the LC n-3 PUFA fish oil Lovaza from GlaxoSmithKline (omega-3-acid ethyl esters; a combination of ethyl esters of eicosapentaenoic acid (EPA) and docosahexaenoic acid (DHA)) in obese non-diabetic adults, to determine if LC n-3 PUFA decreases adipose CCL2-CCR2 and CX3CL1-CX3CR1, alters circulating monocyte and ATM phenotype, and stimulates GPR120 signaling and NFκB attenuation. We will explore the relationship between the oral microbiome and metabolic and inflammatory parameters at baseline, as well as the effect of LC n-3 PUFA supplementation on the oral microbiome composition.

We have chosen Lovaza at 4 grams/day (1860 mg EPA and 1500 mg DHA) for 8 weeks based upon anti-inflammatory effects noted in our preliminary data. A relatively young and healthy population was chosen to remove risk of chronic disease and medication use, yet subjects will be obese to enrich for low grade chronic adipose and systemic inflammation where LC n-3 PUFA are expected to have greater impact. Our previous work shows elevated CX3CL1 protein levels in obese adipose¹⁵, while elevated CCL2 and macrophage infiltration with obesity is established^{13-15,58}.

3.0 STUDY OBJECTIVES

Hypotheses

Primary

1. Omega-3 fatty acid supplementation for eight weeks reduces systemic chemokine signaling (plasma levels of CX3CL1).

Secondary

1. Omega-3 fatty acid supplementation will attenuate systemic and adipose tissue inflammation and leukocyte activation.
 - a. Additional circulating inflammatory chemokines and cytokines levels e.g., IL-6, MCP-1, CCL5, TNFalpha
 - b. Circulating monocyte subpopulations (ratio of inflammatory CX3CR1^{low}CCR2⁺ to less inflammatory CX3CR1^{hi}CCR2⁻)
 - c. Protein levels and mRNA expression of adipose tissue inflammatory chemokines and cytokines (CX3CL1, MCP-1, IL6, TNFalpha, CCL5)
 - d. Adipose tissue macrophage phenotype (ratio of inflammatory M1 to regulatory M2 macrophages, relative T-cell quantification)
2. Changes in chemokine signaling will correlate with improvements in metabolic parameters
 - a. Decreases in plasma lipids
 - b. Decreases in fasting glucose, insulin and homeostasis model assessment for IR (HOMA-IR), a marker of insulin resistance

Exploratory

1. Omega-3 fatty acid supplementation will decrease indirect markers of GPR120 and NFκB action. Adipose protein levels of IκB and total/phospho-TAK1 will be assessed as well as GPR120 mRNA expression and protein levels will also be quantified,

2. Any effects seen on GPR120 and NF κ B action will be correlated to serum and urine DHA and EPA levels.
3. Omega-3 fatty acid supplementation will cause changes in oral microbiome (bacterial DNA composition).
4. Baseline composition and treatment-related change in oral microbiome composition will be correlated to dietary history (as recorded in dietary recall and food frequency questionnaire) as well as to metabolic parameters
5. Subject's genotype at GPR120 and other loci involved in omega-3 action, inflammatory signaling, and nutrient sensing will affect response to treatment.

Objectives: Compared to placebo, we will examine the effect of omega-3 fish oil supplementation in obese subjects on:

Primary:

- 1) Plasma levels of CX3CL1

Secondary:

- 2) Additional plasma cytokines and chemokines
- 3) Circulating monocyte subpopulations
- 4) Adipose tissue cytokine and chemokine levels
- 5) Adipose tissue macrophage subpopulations
- 6) Plasma lipids, insulin, glucose, and HOMA-IR

Exploratory:

- 7) Adipose protein levels of I κ B and total/phospho-TAK1
- 8) GPR120 mRNA expression and protein levels
- 9) serum and urine DHA and EPA levels
- 10) Oral microbiome bacterial DNA composition
- 11) GPR120 genotype

4.0 STUDY DESIGN AND RATIONALE

We propose to conduct a parallel arm, double blind, placebo-controlled trial to understand the anti-inflammatory and metabolic effects of marine derived omega-3 fatty acids (EPA + DHA) on obesity-related inflammation and chemokine signaling in humans. Obese (BMI > 30 kg/m²) but non-diabetic young males and females (n ~ 44; 25 to 50 years of age) taking no omega-3 fatty acid (EPA + DHA) supplements and consuming a low fish diet (defined as usual intake of high omega-3 fish (tuna and other non-fried fish) < 3 to 4 servings per month) will be included. A low habitual fish intake is important to control EPA + DHA intake during the supplement period (see exclusion criteria below). Subjects also will be required to maintain their current fish intake throughout the treatment period.

There will be two treatment groups; (1) placebo and (2) omega-3 fatty acids 4 grams/day. The trial will be randomized, double blind, placebo-controlled, with parallel treatment groups; treatment with omega-3 fatty acids 8 weeks. We will enroll participants until at least 22 subjects per study-arm complete all study visits (i.e., at least 44

participants).

4.1 Drug, Dose Selection and Duration

Prescription Lovaza (omega-3-acid ethyl esters) from GlaxoSmithKline at 4 grams day (2 1-gram capsules twice daily, with food) will be used. We expect this dose to be safe because it is a dose that is recommended, and routinely used, for management of moderate or worse hypertriglyceridemia (levels ≥ 400 mg/dL). We will use matching placebo capsules so that all participants are taking 2 capsules twice daily – with food as recommended in clinical practice.

The study duration was chosen in order to provide adequate time for potential anti-inflammatory effects of treatments without requiring maximum lipid modifying effects while also reducing the potential for drop-out and loss to follow up that is associated with longer study durations.

5.0 SUBJECT POPULATION

5.1 Number of Subjects

We will enroll 22 subjects per arm for a total of 44 subjects completing. Based on prior experience with similar studies we anticipate a drop-out/failure to adhere rate of $\leq 20\%$. Therefore, we estimate that we will randomize ~52 (~26 per arm) subjects to reach our desired sample size.

5.2 Source of Subjects

Participants will be recruited from the Preventive Cardiology Research databases, comprised of healthy subjects who have participated in previous research studies and who have asked to be contacted for future studies. Potential participants will also be recruited via local IRB-approved flyers, internet, and newspaper advertisements (see flyer and advertisement attached) targeting the Delaware Valley region.

5.3 Inclusion Criteria

To be eligible for enrollment in this study, participants must meet all of the following criteria:

1. Men and non-pregnant/lactating women between the ages of 18 and 50.
2. BMI ≥ 30 kg/m²
3. Participants who are able to give written informed consent and willing to comply with all study-related procedures.

5.4 Exclusion criteria

1. Diabetes Mellitus (glucose fasting >126, or random >200, or use of any anti-diabetic agent)
2. Self-reported fish or shellfish allergy
3. Planned usage of any prescription or non-prescription anti-inflammatory, antibiotic, glucose-lowering, lipid modulating or otherwise relevant medication during the study period.
4. Recent (within 6 months) use of LC n-3 PUFA or fish oil supplements or self-reported dietary intake of >3 servings of fish/month
5. Blood pressure >140/90
6. Recent (within 6 months) use of statins, niacin, or fenofibrates
7. Current or planned pregnancy/lactation. Pre-menopausal women unwilling to prevent pregnancy by use of the following approved contraceptive strategies: diaphragm, cervical cap, condom with spermicide, surgical sterility, birth control pills, Depo-Provera injection, IUD, progestin implant, or abstinence.
8. History of liver disease or abnormal LFTs (AST, ALT, Alk. Phos; bilirubin > 2x ULN) at Screening Visit
9. Men who are unwilling to limit alcohol consumption to < 14 alcoholic drinks per week or < 4 alcoholic drinks per occasion (AMA / NIAAA criteria for “at risk” usage levels) while participating in the study
10. Women who are unwilling to limit alcohol consumption to < 7 alcoholic drinks per week or < 3 alcoholic drinks per occasion (AMA / NIAAA criteria for “at risk” usage levels) while participating in the study.
11. Hemoglobin less than 11.0 g/dL
12. Any reported arrhythmia, usage of anti-arrhythmic therapy, or abnormal screening electrocardiogram
13. Known bleeding disorder or coagulopathy
14. Any major active rheumatologic, pulmonary, hematologic or dermatologic disease or inflammatory condition or minor active infection
15. Self-reported history of HIV positive
16. Patients who have undergone any organ transplant

17. Individuals who currently use tobacco products or have done so in the previous 30 days
18. Treatment with aspirin, NSAIDs, COX-2 inhibitors, steroids or any immunomodulatory therapy 2 weeks prior to the Screening Visit
19. Participants who are unwilling to eliminate omega-3 fatty acid (EPA + DHA) supplements and/or fortified food, or have their usual intake of high omega-3 fish (tuna and other non-fried fish) be > 3 to 4 servings per month as assessed by a simple screening questionnaire
20. Recent (within 6 months) treatment with coumarin-type anticoagulants
21. Positive urine pregnancy test result.
22. Self-reported history of injected recreational drug use.
23. Any medical condition or abnormal laboratory value that is judged clinically significant by an investigator

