6.5.3 Telephone / E-mail Follow up (Visit 3)

Participants will be contacted by telephone or e-mail approximately four weeks (visit 3) post-randomization to review medication compliance and pill diary, adverse events and any changes in fish consumption. Participants with <80% apparent adherence to study medication will be counseled to increase compliance so that their adherence at 8 weeks will be $\geq 80\%$.

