6.6 Study Discontinuation/Completion

A subject may be withdrawn from the study at any time at either the investigator's discretion or the subject's request. An effort must be made to document the reason(s) why a subject fails to return to the study clinic for necessary visits or is discontinued from the study. The primary reason for discontinuing participation in the study must be stated and may include, but is not limited to, one of the following:

- ◆ Development of any abnormality in blood counts, blood chemistries, or urinalysis because of which the investigator deems continued participation in the study to be ill-advised
- ◆ Use of unapproved concomitant medications

- ◆ Occurrence of intolerable AEs
- ◆ Development of LFT abnormalities (>1.5 ULN), unexplained muscle aches/myopathy, kidney dysfunction (Cr>ULN), or significant bleeding (e.g. GI bleed, cerebral hemorrhage, major ENT bleed).
- ◆ Withdrawal of consent by patient
- ◆ Noncompliance with protocol, e.g., the patient fails to appear at one or more visits
- ◆ Non adherence with study medications – defined as failure to take >80% of study medications (pill count and diaries)
- ◆ Development of an intercurrent illness, injury, or medical condition likely to interfere with patient safety, the overall assessment, or the required administration of study medication
- ◆ Development of any condition for which the investigator feels treatment withdrawal is justified
- ◆ Termination of the study by the sponsor (NIH)

The procedure to discontinue a subject from the study is as follows:

- ◆ record any AEs since previous visit
- ◆ record any medications
- ◆ record vital signs
- ◆ perform a physical examination (if discontinuation is due to an AE)
- ◆ collect blood for clinical laboratory analysis

Patients who discontinue from the study because of an AE(s) should be treated and followed according to established medical practice.

The study may also be discontinued at the discretion of the Principal Investigator, if any safety concerns are identified during the course of the study.

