In some patients, increases in alanine aminotransferase (ALT) levels without a concurrent increase in aspartate aminotransferase (AST) levels were observed. ALT levels will be monitored before and after LOVAZA treatment. If a subject's ALT level is greater than 1.5 x ULN, then the subject will be excluded from the study.

In some patients, LOVAZA increased low-density lipoprotein cholesterol (LDL-C) levels. This tends to be most notable in patients with more severe hypertriglyceridemia in whom Lovaza causes the greatest redistribution of cholesterol from VLDL to LDL particles coincident with reduction in triglyceride rich VLDL particles. In such patients, Lovaza increases the size and composition of LDL from small, dense particles (which are thought to be atherogenic due to their susceptibility to oxidation), to large buoyant particles. These larger particles have a greater affinity for cholesterol receptors and are catabolized rapidly. Indeed, total cholesterol in atherogenic apoB lipoproteins (e.g., estimated by calculation of non-HDL cholesterol) tends to fall on Lovaza consistent with redistribution of cholesterol from VLDL to LDL with increased size of LDL particles rather than any overall increase in atherogenic apoB-cholesterol containing particles [10-13]. Thus we will exclude from participation any subject with LDL-C at screening of greater than 190 mg/dl and LDL-C will be repeated at completion of the study (visit 4).

The most common adverse effects reported with LOVAZA are burping, infection, flu symptoms, upset stomach, a change in sense of taste, back pain and skin rash. Monitoring for these adverse events will be conducted at the follow-up Visit 3 (telephone / email visit at 4 weeks post randomization). If these events worsen and/or become extremely bothersome over time, the subject will be discontinued from the study as outlined below in Section 6.1.

There is a possible association between LOVAZA and more frequent recurrences of symptomatic atrial fibrillation or flutter in patients with paroxysmal or persistent atrial fibrillation, particularly within the first months of initiating therapy. We will exclude from the study any subject with diagnosis of cardiac arrhythmias or abnormal ECG on screening. ECG will be repeated at completion of study (visit 4) and any new arrhythmia noted as an adverse event.

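### Section 5.4 and the Safety Plan disagree on eligibility: 5.4 lacks the LDL-C limit, its liver-test limit is ambiguous, and the Safety Plan credits it with a medication rule it does not contain

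*Combined protocol and SAP*

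**What the plan says.** **LDL-C.** Safety Plan 3.2 (Appendix D) states that "we will exclude from participation any subject with LDL-C at screening of greater than 190 mg/dl". Section 5.4 has no matching item. The nearest is item 23, which excludes "Any medical condition or abnormal laboratory value that is judged clinically significant by an investigator".

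**ALT.** Item 8 of 5.4 excludes "History of liver disease or abnormal LFTs (AST, ALT, Alk. Phos; bilirubin > 2x ULN) at Screening Visit". Safety Plan 3.2 says that "ALT levels will be monitored before and after LOVAZA treatment" and that if a subject's "ALT level is greater than 1.5 x ULN, then the subject will be excluded from the study". Section 6.6 (Study Discontinuation/Completion) lists "Development of LFT abnormalities (>1.5 ULN" among the reasons for withdrawal.

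**Medication.** Safety Plan 2.0 cites Section 5.4 as excluding anyone on a regular medicine other than contraception. The broadest medication item in 5.4 is item 3: "Planned usage of any prescription or non-prescription anti-inflammatory, antibiotic, glucose-lowering, lipid modulating or otherwise relevant medication during the study period".

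**Timing.** Appendix A places the metabolic panel (which includes ALT) and the lipid profile at Visits 1 and 4. Section 7.1 places the baseline ALT and LDL-C at Visit 2, with a repeat at completion. Section 6.5.3 makes Visit 3 a remote contact: "Participants will be contacted by telephone or e-mail approximately four weeks (visit 3) post-randomization".

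**The concern.** Screening staff would normally work from the numbered criteria in 5.4. If that list is incomplete or can be read in two ways, a volunteer can satisfy it and still be someone the Safety Plan says must not enter. Under Safety Plan 3.6 the DSMB judges conduct against the Safety Plan, so enrolment that complies with 5.4 could count as a departure.

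ALT and LDL-C are the two laboratory risks that Section 7.1 names for the drug. Neither has a scheduled test between the first dose and Visit 4, so entry is the only scheduled point at which a limit on either can prevent exposure. Safety Plan 5.1 ties the definition of a significant laboratory abnormality to the screening criteria, so an unclear item 8 may also blur what counts as an adverse event.

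On medication, Section 2.0 gives avoidance of medication use as one reason for choosing this population. Section 6.6 permits withdrawal for unapproved medicines without defining them.

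**Working it through.** There is no sample-size or test arithmetic to reproduce. The check sets the texts side by side.

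**1. LDL-C.** Of the 23 items in 5.4, 0 set an LDL-C limit. Items 3 and 6 concern lipid drugs, not lipid levels. Take a volunteer with screening LDL-C of 200 mg/dl:
- Safety Plan 3.2: 200 > 190, excluded.
- Section 5.4: eligible, unless an investigator chooses to invoke item 23.

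**2. ALT.** Item 8 has two readings. On the wide reading, the 2x multiple governs all four tests. On the narrow reading, the semicolon confines it to bilirubin, and any abnormal AST, ALT or alkaline phosphatase excludes. The table takes abnormal ALT to mean above ULN and applies the Safety Plan limit at entry.

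| Screening ALT (x ULN) | 5.4, wide reading | 5.4, narrow reading | Safety Plan 3.2 |
|---|---|---|---|
| up to 1.0 | eligible | eligible | eligible |
| above 1.0 to 1.5 | eligible | excluded | eligible |
| above 1.5 to 2.0 | eligible | excluded | excluded |
| above 2.0 | excluded | excluded | excluded |

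On the wide reading, 5.4 admits the third row and the Safety Plan does not. A volunteer there can start at up to 2.0/1.5 = 1.33 times the value that 6.6 gives as a reason to withdraw. On the narrow reading, 5.4 admits nobody whom the Safety Plan excludes; it is the stricter text, and the difference is confined to the second row.

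**3. Scheduled tests after the first dose.** Under Appendix A (Visits 1 and 4) or Section 7.1 (Visit 2 and completion), the number of scheduled ALT or LDL-C tests between the first dose and Visit 4 at week 7-9 is 0.

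**4. Medication.** The items in 5.4 that concern drugs or supplements are:
- 1: anti-diabetic agents
- 3: listed classes plus an undefined class of other relevant medicines
- 4 and 19: omega-3 products
- 6: statins, niacin, fenofibrates
- 12: anti-arrhythmics
- 18: aspirin, NSAIDs, COX-2 inhibitors, steroids, immunomodulators
- 20: coumarin-type anticoagulants

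None is a general bar on regular medicines. A volunteer taking a regular medicine outside these classes, and not judged relevant under item 3, is eligible under 5.4 but excluded by the Safety Plan's account of it.

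**The case against.** **The LDL-C limit is already in the protocol.** Appendix D is attached to it, Sections 7.0, 11.0 and 13.0 send the reader there for safety detail, staff are to be trained on the exclusion criteria, and item 23 is a backstop. This is largely right: the limit is missing from 5.4, not from the protocol. But item 23 permits exclusion without requiring it, whereas Safety Plan 3.2 leaves no discretion, so the gap in the working list remains.

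**Item 8 is already the stricter rule.** The semicolon makes the narrow reading a natural one. The 1.5x value in 6.6 concerns abnormalities that develop on study, and Safety Plan 3.5 also uses it for on-study findings. A coherent scheme is therefore available: any abnormal ALT bars entry, and 1.5x triggers action later. This stands. It can be answered that a purely on-study rule would have no scheduled result to act on before completion, and that ALT is to be checked before treatment as well as after. That is not decisive, because Safety Plan 6.1 also lists a reason judged at Visit 4 (pill count). A reader might infer that 5.4 definitely admits ALT of 1.5-2 times ULN, or that item 8 should simply be reset to 1.5x. The documents support neither, and on the narrow reading that reset would let in volunteers at 1.0-1.5 times ULN who are now excluded.

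**The Safety Plan is the weaker source.** It is dated June 2013 against November 2014 for the protocol, and its Section 3.5 describes an inpatient endotoxemia visit that is not part of this trial. That is a reason not to let its figures overwrite 5.4 without clinical confirmation. It does not remove the mismatch, because the plan is a current appendix.

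**The medication point is editorial.** Mostly so. Safety Plan 2.0 is a loose summary, item 3 gives latitude, and no harmful medicine admitted by 5.4 has been identified. What stands is that the summary misstates the section it cites.

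**Conclusion.** The two texts disagree, and the three parts carry different weight.

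- **LDL-C:** a clear omission from 5.4, 0 of 23 items against an explicit 190 mg/dl limit in Safety Plan 3.2.
- **ALT:** an ambiguity. The band of 1.5-2 times ULN, and the 1.33 ratio to the withdrawal value, exist only if the 2x multiple covers all four tests and the Safety Plan sentence applies at entry. If the multiple covers bilirubin alone, there is no gap.
- **Medication:** a misstatement in Safety Plan 2.0 of what 5.4 contains.

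The consequence is for safety and consistent eligibility. A reader might infer that the primary comparison is compromised. It is not: entry rules act before randomisation, so they do not bias the comparison between arms, and the power calculation does not depend on them. The documents give no basis for counting affected volunteers. Item 23, the approved dose and the short treatment period all limit the likely harm. This should be corrected, but it does not threaten the trial.

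**What to change.** Make 5.4 the single eligibility list and have Appendix D refer to it.

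1. Add screening LDL-C above 190 mg/dl as an exclusion in 5.4.
2. Rewrite item 8 with one explicit limit for each of AST, ALT, alkaline phosphatase and bilirubin, such that nobody can enter with ALT above 1.5 times ULN. If the intended rule is that any ALT above ULN excludes, state that and keep it; do not relax it to 1.5x.
3. Have the sponsor confirm which medication rule applies: no regular medicines except contraception, or named classes only. Use identical wording in item 3 and Safety Plan 2.0, and use it to define an unapproved medicine in 6.6.

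The cost is one amendment with matching text in Appendix D. ALT, LDL-C and the medication review are already done at Visit 1 (Appendix A), so no test is added. The LDL-C limit will produce a few more screen failures. The ALT change adds some only if item 8 has been applied at 2x to all tests. The medication change adds some only if the sponsor adopts the strict rule.
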